10.3 Stratification Factors

N/A

10.4 Analysis of Secondary Endpoints

Descriptive statistics and graphical displays will be used to evaluate correlation between response and trough levels and pharmacodynamics of sEphB4-HSA. Depending on the number enrolled, the association between clinical response and changes in trough levels, pharmacodynamic endpoints, including indicators of changes in VEGF-Notch-EphrinB2 angiogenic pathway, viral copy number, protein expression and activation status, and finally immune cell counts, and activation status will be investigated using the nonparametric Wilcoxon rank sum test.

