1.2 Secondary Objectives

1.2.1 To assess the safety of sEphB4-HSA in participants with KS.

1.2.2 To determine trough level exposure of sEphB4-HSA and correlate with tumor response.

1.2.3 To characterize the pharmacodynamics of sEphB4-HSA and correlate these effects with clinical response.

1.2.3.1 Effects on viral replication and gene expression of HHV-8.

1.2.3.2 Changes in VEGF-Notch-EphrinB2 angiogenic pathway.

1.2.3.3 Effects on immune response and modulation.

1.2.3.4 Effects on tumor cell apoptosis and proliferation.

1.2.3.5 Effects on sEphB4-HSA on Human Immunodeficiency Virus (HIV) plasma viral loads in participants with HIV.

1.2.4 To archive peripheral blood mononuclear cells (PBMCs) and tissue samples to be used in conjunction with samples collected in subsequent trials of sEphB4-HSA for future studies including identification of biomarkers predictive of response.

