- 8.1.9 Tumor assessments with photographic record must be performed prior to initiating treatment. These may be performed on Day 1, but no earlier than 7 days before initiating study treatment. Tumor assessments should include the following:
- Identify marker lesions: Select five bi-dimensionally measurable marker lesions for assessing changes in lesion dimension. Select the largest lesions with clearly defined margins. Marker lesions will be photographed as described in [Appendix VI](#).
 - Participants should have a sufficient number of non-indicator lesions available for biopsy of a size that will permit four 5-mm tumor biopsies during the study (two biopsies will be performed on Day 1 **prior to** treatment in Cycle 1 and two biopsies will be performed on Day 15 of Cycle 1 **after completion of one cycle**) (biopsies may be performed up until Day 1 of Cycle 2). The two biopsies can be performed on two separate non-indicator lesions measuring > 5 mm OR performed on one non-indicator lesion measuring >10 mm in size.
 - For participants with ≤ 50 total skin and oral lesions, all lesions must be evaluated for changes in number and characteristics. For participants with > 50 total skin and oral lesions, choose three representative areas, for evaluating change in lesion numbers and characteristics (preferably an area with ≥ 5 lesions). **These areas will be photographed as described in [Appendix VI](#).**

NOTE: A representative area is a single extremity, the back, chest, or face that has lesions similar in characteristics (i.e., nodularity, size, color, and number) to those found on other parts of the body. A representative area does not need to be the area with the largest number of lesions but should contain lesions that are truly representative of those throughout the remainder of the body.

- 8.1.10 Staging criteria (to be done within 28 days prior to study enrollment): KS staging will be based on the modified AIDS Clinical Trials Group (ACTG) Oncology Committee Staging Criteria ([Appendix VII](#)).
- 8.1.11 Functional assessment of HIV infection (FAHI) + Kaposi sarcoma (KS) QOL questionnaire ([Appendix XII](#)). Those who have HIV-negative KS will not have the HIV portion scored. This may be done within 14 days of starting the study drug up until Day 1 of Cycle 1.

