9.1 Definition of Response

Response and progression will be evaluated in this study using the ACTG response criteria.

9.1.1 Complete response: CR is defined as the absence of any detectable residual disease, including tumor-associated edema, persisting for at least 4 weeks. In participants, in whom pigmented (brown or tan) macular skin lesions persist after apparent CR, biopsy of at least one representative lesion is required in order to document the absence of malignant cells. In participants known to have had visceral disease, an assessment at restaging with appropriate endoscopic or radiographic procedures should be made.

9.1.2 Partial response (PR) is defined as no new lesions (skin or oral), or new visceral sites of involvement (or the appearance or worsening of tumor-associated edema or effusions); AND

- A 50% or greater decrease in the number of all previously existing lesions lasting for at least 4 weeks; OR
- Complete flattening of at least 50% of all previously raised lesions (i.e., 50% of all previously nodular or plaque-like lesion become macules); OR
- A 50% decrease in the sum of the products of the largest perpendicular diameters of the marker lesions.

Note: Participants with residual tumor-associated edema or effusion who otherwise meet the criteria for complete response will be classified as having a PR.

9.1.3 Stable disease is defined as any response not meeting the criteria for CR, PR, or

progressive disease.

9.1.4 Progressive disease (PD) is defined as follows:

For participants with ≤ 50 cutaneous lesions

- 25% increase in the sum of perpendicular diameters of the indicator lesions, OR
- $\geq 25\%$ increase in the total lesion count, or a minimum of 5 new lesions, whichever is greater, OR
- $\geq 25\%$ increase in the number of raised lesions (minimum of 5 new raised lesions if there are very few raised lesions, for example ≤ 8), whichever is greater.

Note: There are body sites where disease is particularly difficult to evaluate, and a few new lesions may be counted in spite of the fact that a participant is not actually progressing. For example, lesions of the foot, particularly those which are flat, are difficult to evaluate because their intensity may be variable based on how much edema is present, how much the person walked the day before, how long their feet have been in a dependent position prior to the physical exam, etc.

For participants with > 50 cutaneous lesions

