10.2 Sample Size/Accrual Rate

A total of 20 evaluable participants will be enrolled. The design was developed by considering the joint probability of clinical response and toxicity simultaneously (Jin H. Alternative designs of phase II trials considering response and toxicity, *Contemp Clin Trials* 28 (2007): 525-53). The null hypothesis for defining the unacceptable region based on clinical response rate and toxicity rate simultaneously and the alternative hypothesis for defining the region for a promising agent are as follows:

- $H_0: P_{\text{resp}} \leq 0.30 \text{ OR } P_{\text{tox}} \geq 0.30$
- $H_1: P_{\text{resp}} \geq 0.60 \text{ AND } P_{\text{tox}} \leq 0.10$

In a single stage design, 20 participants will be evaluated for clinical response and toxicity. Toxicity will be defined as: unacceptable toxicities as defined in [Section 10.1](#). All unacceptable toxicities that are possibly, probably, or definitely attributed to protocol therapy will be counted as a toxicity.

The null hypothesis will be rejected if there are at least 9 responders, and no more than 3 participants who experience unacceptable toxicities. This design has power of 0.82 and a significance level of 0.11. The planned accrual rate will be one participant per month.

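### Section 10.4 formally tests exposure and biomarker associations only against responder yes/no; a graded response analysis beside the Wilcoxon test would use data already collected and gain power

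*Combined protocol and SAP*

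**What the plan says.** Objective 1.2.2 is "To determine trough level exposure of sEphB4-HSA and correlate with tumor response". Objective 1.2.3 asks for pharmacodynamic effects to be correlated with clinical response.

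Section 10.4 starts with descriptive statistics and graphical displays. Depending on how many participants enroll, it then tests the association between clinical response and changes in trough levels and in the pharmacodynamic markers; these, down to "immune cell counts, and activation status will be investigated using the nonparametric Wilcoxon rank sum test". No other formal test is named. Section 9.0 reports clinical response as CR or PR, so the test compares responders with non-responders.

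The graded information is already in the trial. Section 8.1.9 says: "Select five bi-dimensionally measurable marker lesions for assessing changes in lesion dimension". It also has lesion number and characteristics evaluated, on all lesions or, above 50 lesions, in three representative areas. Sections 8.2.2.1 and 9.0 repeat the tumor assessment on Day 1 of every cycle. Section 9.1.2 gives three alternative routes to PR: at least a 50% fall in lesion number, complete flattening of at least half the raised lesions, or "A 50% decrease in the sum of the products of the largest perpendicular diameters of the marker lesions".

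Section 2.5 calls the correlative studies exploratory. Section 10.4 gives them no alpha, power or effect size.

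**The concern.** A two-group test ignores how far a participant moved within each group. A participant just short of every PR threshold counts the same as one who progressed, and a bare PR counts the same as a CR. With 20 participants, that is a real share of the information.

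What is at stake is the yield of the correlative program. Section 2.5 makes biopsies before and during treatment mandatory, acknowledges that they do not directly benefit the participant, and justifies them by mechanism and by candidate predictive markers for later trials. A relation that is present but missed weakens that justification. Leaving the graded analysis unspecified also leaves the choice of outcome scale open until the data are seen.

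**Working it through.** **1. The plan's own figures.** Section 10.2: "A total of 20 evaluable participants will be enrolled"; "The null hypothesis will be rejected if there are at least 9 responders, and no more than 3 participants who experience unacceptable toxicities". Taking response and toxicity as independent:

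- Power = P(X ≥ 9 | 20, 0.60) × P(T ≤ 3 | 20, 0.10) = 0.9435 × 0.8670 = 0.818 (stated 0.82).
- Significance level = larger of P(X ≥ 9 | 20, 0.30) = 0.1133 and P(T ≤ 3 | 20, 0.30) = 0.1071, so 0.113 (stated 0.11).

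Both reproduce. They concern the primary decision only.

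**2. Inputs for the secondary tests.** From the documents: n = 20; response rates of 0.30 and 0.60 from the two hypotheses, with 0.45 between them; three PR routes. Assumed, because the documents give no values: two-sided alpha 0.05, marker correlation ρ, correlation λ between routes, and the shares with CR and PD.

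**3. Simplest case: response is a cut of marker-lesion area.** Marker and area change are bivariate normal with correlation ρ. The exact rank sum test on responder status is compared with Spearman on area change, over response rates 0.30 to 0.60.

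| ρ | Rank sum | Spearman, area | Gap (points) |
|---|---|---|---|
| 0.4 | 0.23–0.26 | 0.38–0.39 | 12–15 |
| 0.5 | 0.36–0.40 | 0.57–0.58 | 18–22 |
| 0.6 | 0.51–0.58 | 0.77 | 20–26 |

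This is where a figure of 12 to 26 points comes from. Section 9.1.2 does not define response this way.

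**4. Three routes, as in Section 9.1.2.** For area, count and flattening, Mⱼ = √λ·L + √(1−λ)·eⱼ, where L is a shared benefit. A participant responds if the largest Mⱼ exceeds the cut that gives the chosen response rate. The marker is x = ρ·z + √(1−ρ²)·ε, where z is the (standardized) best route, flattening only, or L. The ordered category cuts the best route again, with 5% CR and 15% PD. Spearman uses t = r√(18/(1−r²)) on 18 degrees of freedom. There are 10,000 trials per cell, so each power has a standard error of at most √(0.25/10,000) = 0.005.

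Gain over the rank sum test in points, for ρ 0.4–0.6, λ 0.3–0.9 and response rate 0.30–0.60:

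| Marker follows | Ordered category | Best-of-routes change | Area alone |
|---|---|---|---|
| Best route | +8 to +20 | +12 to +27 | −21 to +22 |
| Flattening only | +3 to +19 | +5 to +26 | −13 to +19 |
| Shared benefit L | +3 to +18 | +5 to +25 | +1 to +23 |

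Example (best route, ρ = 0.6, λ = 0.5, response rate 0.30): rank sum 0.51, ordered category 0.69, best-of-routes change 0.77.

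The low ends in the last two rows come from loosely linked routes (λ = 0.3) and ρ = 0.4. Changing the shares to 5–10% CR and 25–30% PD moves the first ordered-category range to about 7 to 22.

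**5. Where area alone loses.** At ρ = 0.6 and λ = 0.3, area has power of about 0.11 against 0.21–0.24 for the rank sum test if the marker follows flattening. If it follows the best route, the figures are about 0.35 against 0.50–0.56.

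**6. Size under no association.** The exact rank sum test rejects about 4% of the time and Spearman about 5%, so roughly one point of each gap reflects the discreteness of the exact test.

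**The case against.** The strongest defense is that Section 10.4 answers the objectives as written. Objective 1.2.3 says clinical response, and Section 9.0 defines that as CR or PR. The formal test follows descriptive and graphical work that is not limited to yes/no response. The analyses are declared exploratory and drive no decision. All of this stands, and it is why the responder comparison should stay and why nothing here is an error. It does not show that the graded data should go without a prespecified analysis; Objective 1.2.2 refers more broadly to tumor response.

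A reader might infer that the Wilcoxon test costs 12 to 26 points against marker-lesion area, and that area should become the main outcome. The documents do not support this. Response can be reached by count or flattening, so it is not a cut of area, and step 5 shows that area alone can do worse. Area at one fixed visit also misses later response, which Section 9.0 allows to count.

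A reader might also infer that a 45% shrinkage in area is always treated like growth. That is so only if neither other PR route is met.

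**Conclusion.** The point holds as an efficiency gap in exploratory analyses. The only formal test uses responder yes/no, while graded response is recorded every cycle.

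For n = 20, two-sided 5% and a marker correlated 0.4 to 0.6 with the graded response produced by the three routes, the loss is roughly 8 to 27 points of power. The lower end is for the ordered category and the upper end for the best-of-routes change. If the marker follows a single route or only a shared benefit, and the routes are loosely related, the loss can be as small as about 3 points. A graded measure covering all routes was ahead in every scenario run. The correlations, alpha and category shares are assumptions, so the direction is firmer than the size.

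The documents do not support reading this as a flaw in the stated power of 0.82 or significance level of 0.11, which reproduce and are unaffected.

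**What to change.** In Section 10.4, keep the Wilcoxon responder comparison and add beside it:

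- A Spearman correlation (or trend test) of trough level and of each pharmacodynamic change with the ordered response category, CR > PR > SD > PD, using the same response assessment as the Wilcoxon comparison. State where the early-death and not-assessable categories of Section 10.7 are placed.
- As support, Spearman correlations with percent change from baseline to Cycle 3 Day 1 in the marker-lesion sum of products, total lesion count and raised-lesion count. For participants with more than 50 lesions, take the counts from the representative areas of Section 8.1.9.

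Do not make marker-lesion area alone the main analysis.

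The cost is SAP wording and a few more exploratory tests per marker, which adds to the number of chance findings and should be acknowledged when results are reported. No new data, visits or samples are needed.

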10.5 Analysis of Exploratory Endpoints

Using the FAHI+KS questionnaire, pain and swelling improved in AIDS-KS patients treated with paclitaxel or pegylated liposomal doxorubicin on AMC009/ECOG E1D96 protocol.¹⁸ Significant improvements in social well-being and cognitive functioning were also reported. Thus, there is an interest in assessing QOL changes after baseline in this study using the same instrument to facilitate comparisons with the previous study.

In the FAHI+KS questionnaire, 5 measures of overall QOL will be scored: physical well-being, emotional well-being, functional and global well-being, social well-being, and

cognitive functioning. The questionnaire will be collected at baseline, cycle 4, and end of treatment. General estimating equations will be used to evaluate changes in the 5 measures of overall QOL over time adjusting for intra-participant variation. There are three supplemental statements regarding participant perception of KS-specific symptoms: pain, swelling. Agreement with each of these statements is graded using a Likert scale from 0 to 4. Responses to these statements may be dichotomized to reflect positive or negative impact of these symptoms. General estimating equations using a log-binomial model will be used to assess changes in these symptoms over time.

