1.3 Exploratory Objective

Describe baseline quality of life (QOL) scores, using the functional assessment of HIV Infection (FAHI) + Kaposi sarcoma (KS) questionnaire, in participants with KS, and explore changes in QOL of participants on treatment with sEphB4-HSA.

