- 8.2.2.10 Biologic endpoints: peripheral blood for biologic endpoints described in [Appendices I](#) and [III](#) will be collected at Day 1 of Cycles 2, 4, 6, 7, and 10. The samples include blood for immune studies on Day 1 of Cycles 2, 4, and 6 to be done before study treatment dosing. Given this will be a fresh blood sent at room temperature overnight, if the blood for immune studies cannot be collected on Monday-Wednesday (i.e., the dose is administered on Thursday or Friday), this blood work can be obtained the Monday AFTER the dose was given. Blood for HHV-8 viral loads and archived research purposes on Day 1 of Cycles 4, 7, and 10, and at treatment discontinuation.
- 8.2.2.11 Biologic endpoints: peripheral blood for pharmacokinetics as described in [Appendices I](#) and [II](#) will be collected on Day 1 and 15 of Cycle 2; the samples will be drawn pre-dose.
- 8.2.2.12 If HIV positive, T-lymphocyte subsets (CD4 and CD8) to be done every three cycles (Day 1 of Cycle 4, 7, and 10), and at treatment discontinuation.
- 8.2.2.13 If HIV positive, HIV-1 plasma RNA to be done every three cycles (Day 1 of Cycles 4, 7, and 10), and at treatment discontinuation).
- 8.2.2.14 FAHI+KS quality of life questionnaire on Day 15 of Cycle 4 (questionnaire may be performed up until Day 15 of Cycle 5). Those who have HIV-negative KS will not have the HIV portion scored. See [Appendix XII](#) for KAH1+KA questionnaire.

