8.3 Treatment Discontinuation

At the time of treatment discontinuation, all evaluations should be completed as soon as possible. AEs must be reported to the AMC Operations and Data Management Center if the AE began any time within 4 weeks of receiving the study treatment. Additionally, if a site learns of any incidence of death, cancer, or fetal anomaly, which is possibly, probably, or definitely related to the drug, at any time after treatment discontinuation, the event should be reported to the NCI through CTEP-AERS (see [Section 6.3](#)) within 24 hours of when the investigator learns of the event. This information may provide additional insight into the safety of sEphB4-HSA.

The following procedures should be performed upon discontinuation of study drug:

- CBC with differential.
- Serum chemistries: liver enzymes (AST [SGOT], ALT [SGPT], alkaline phosphatase), BUN, creatinine, electrolytes (sodium, potassium, chloride, bicarbonate, calcium,

phosphorus, glucose), total protein, albumin, bilirubin (direct and indirect).

- Complete physical examination including: vital signs, weight, ECOG or KPS performance status, signs and symptoms review, and toxicity evaluation.
- Review of antiretrovirals and adherence to antiretroviral therapy (if applicable).
- Review of AIDS-defining events.
- KS tumor assessment with photographic records. Response of KS to treatment with sEphB4-HSA will be assessed as described in [Section 9.1](#).
- KS staging ([Appendix VII](#)).
- Biologic endpoints: peripheral blood for biologic endpoints including HHV-8 viral load and peripheral blood for archive research purposes.
- If HIV positive, CD4 and CD8 counts and percentages, quantitative HIV-1 plasma RNA.
- Urinalysis.
- If the participant had documentation of visceral disease while on study, re-evaluation of visceral disease, if not already done while on study. This should be done before the post-treatment evaluation.
- Permanent discontinuation of drug will be documented.

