8.4 Post-treatment Evaluation

All participants must be seen 4-6 weeks after discontinuation or completion of study treatment (counting from Day 28 of the final cycle). If participants are unable to return to the clinic, attempts should be made to obtain follow-up information from the treating physician regarding performance status, tumor status, toxicity, and subsequent care. Participants who withdraw for toxicity reasons should be followed until the toxicity resolves/returns to baseline, or for at least 4 weeks, whichever is later. In addition, participants who go off treatment for reasons other than toxicity should be followed for at least 4 weeks after discontinuing drug.

The following procedures should be performed during the post-treatment evaluation visit:

- CBC with differential.
- Serum chemistries: liver enzymes (AST [SGOT], ALT [SGPT]), alkaline phosphatase, BUN, creatinine, electrolytes (sodium, potassium, chloride, bicarbonate, calcium, phosphorus, glucose), total protein, albumin, bilirubin (direct and indirect).
- Complete physical examination including: vital signs, weight, ECOG or KPS performance status, signs and symptoms review, and toxicity evaluation (AEs must be reported per [Section 6.4](#)).
- Review of AIDS-defining events.
- KS tumor assessment with photographic records if there are any changes from the treatment discontinuation visit. Response of KS to treatment with sEphB4-HSA will be assessed as described in [Section 9.1](#).

- KS staging ([Appendix VII](#)).
- If the participant had documentation of visceral disease while on study, documented re-evaluation of visceral disease.
- FAHI+KS quality of life questionnaire ([Appendix XII](#)). Those who have HIV-negative KS will not have the HIV portion scored.
- At a participant's final study visit the Off-Study Summary Form will be completed.

Telehealth follow-up visits are permitted in the event an in-person visit is restricted and a response evaluation is not required at that visit. The complete physical examination will be deferred (i.e., vital signs, physical); however, symptoms review, and AIDS-defining events review will be conducted via teleconference. If there is any concern of progression or symptoms related to progression of KS, an in-person visit is required to follow the telemedicine visit within 2 weeks.

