APPENDIX I: SCHEDULE OF EVALUATIONS

Baseline evaluations are to be conducted within 21 days prior to start of protocol therapy, unless otherwise specified. Scans and x-rays must be done ≤ 28 days prior to the start of therapy. In the event that the participant's condition is deteriorating, laboratory evaluations should be repeated within 48 hours prior to initiation of the next cycle of therapy. Please note, hypertension is a known and expected side effect of this drug. Please see [Section 5.4](#) for special considerations for participants with cardiac risk factors (history of hyperlipidemia, smoking, diabetes, treatment for hypertension, African American ethnicity) and specific instructions for participants who develop \geq grade 2 hypertension while on treatment.

	Eligibility	Screening/ Baseline	Cycle 1 Day 1	Cycle 1 Day 15	Cycles 2 – 12				Treatment Discont.	Post Treatment Eval.	Follow Up Visits
					Day 1		Day 15				
Informed Consent	X ^a										
Documentation of HIV status		X ^a									
KS Biopsy (Diagnostic)	X ^a										
Complete Medical History		X									
Complete Physical Exam ^s , Complete Review of Signs and Symptoms, and Review of AIDS- defining events		X	X ^g	X ^h	X ^h		X ^h		X	X	X
ECOG or KPS Performance Status	X	X	X ^g	X ^h	X ^h				X	X	
Toxicity Assessment		X ^{bb} (hyper- tension only)	X ^{bb} (hyper- tension only)	X ^{h, bb}	X ^{h, bb}				X	X	
EKG		X ^v									
KS Tumor Assessment, Photographic Record		X ^d	X ^g		X ^{h,r}				X	X ^r	X ^x
Concomitant Medication Review		X	X ^g	X ^h	X ^h						
Assess Adherence to Antiretroviral Therapy	X ^u	X	X ^g	X ^h	X ^h				X		
Review of current and prior anti- HIV therapy (if HIV positive), prior immune based therapy and prior anti-tumor therapy		X	X ^g		X ^h				X		
FAHI+KS Quality of life questionnaire (see Appendix XII)		X ^k	X ^k				X ^m (Cycle 4 only)			X	
KS staging		X ^b							X	X	
CBC with Differential, Serum Chemistries ^l		X	X ^h	X ^h	X ^h		X ^h		X	X	
CD4 and CD8 Count (T Cell Subsets), and HIV-1 plasma		X ^b	X ^l		X ^h (Cycle 4, 7,				X		

	Eligibility	Screening/ Baseline	Cycle 1 Day 1	Cycle 1 Day 15	Cycles 2 – 12				Treatment Discont.	Post Treatment Eval.	Follow Up Visits
					Day 1		Day 15				
RNA, if HIV-positive					10 only)						
HHV-8 Viral Loads (see Appendix III)		X ^{k, y}	X ^{k, y} (predose)		X ^{aa} (Cycle 4, 7, 10 only)				X		
Serum or Urine HCG Pregnancy Test ^c		X ^c	X ^q								
Education and counseling guidance		X ^g									
Dispense sEphB4-HSA			X	X	X		X				

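### Section 10.5 analyses an end-of-treatment quality-of-life score that the visit schedule does not collect; the only late questionnaire is taken off treatment

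*Combined protocol and SAP*

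**What the plan says.** The exploratory objective (1.3) is to describe baseline quality of life and to "explore changes in QOL of participants on treatment with sEphB4-HSA". Section 10.5 gives the data for this: "The questionnaire will be collected at baseline, cycle 4, and end of treatment". Change over time in the five FAHI measures, and in the KS-specific items, is to be modelled with generalised estimating equations (GEE).

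The visit sections schedule the questionnaire as follows.

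- **Baseline (8.1.11):** "This may be done within 14 days of starting the study drug up until Day 1 of Cycle 1".
- **During treatment (8.2.2.14):** "FAHI+KS quality of life questionnaire on Day 15 of Cycle 4 (questionnaire may be performed up until Day 15 of Cycle 5". This is the only collection between baseline and the end of treatment.
- **Treatment discontinuation (8.3):** the list introduced by "The following procedures should be performed upon discontinuation of study drug" does not include it.
- **Post-treatment evaluation (8.4):** the list includes the "FAHI+KS quality of life questionnaire". On timing, 8.4 says: "All participants must be seen 4-6 weeks after discontinuation or completion of study treatment (counting from Day 28 of the final cycle".
- **Follow-up visits (8.5):** not included.

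Appendix I agrees with the text. The row "FAHI+KS Quality of life questionnaire (see Appendix XII" is marked at screening, at Cycle 1 Day 1, at Day 15 for Cycle 4 only, and under Post Treatment Eval. Its cell under Treatment Discont. is empty.

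**The concern.** The analysis section names a time point that neither the visit text nor the calendar collects. If the plan is followed as written, the 8.4 score is the only one that can fill the end-of-treatment slot, and it is taken weeks after dosing has stopped. A score off treatment would then enter the GEE, and probably the report, under an on-treatment label.

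This leaves Cycle 4 as the only on-treatment measurement after baseline. Participants who leave before it, for example for progression or toxicity under 4.5, contribute a baseline score and an off-treatment score, but nothing on how they fared while receiving the drug.

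The protocol gives quality of life some weight. Section 2.2 argues that symptom benefit can be missed by the response categories, and 10.5 keeps the same instrument so that results can be compared with the earlier AMC study. A mislabelled time point weakens both uses.

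**Working it through.** The plan gives no sample size, power or error rate for quality of life, so there is no figure to reproduce. The check compares the schedule with the analysis and then does date arithmetic.

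**Step 1. Match the analysis time points to collections.**

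| Time point in 10.5 | Where collected | State of the participant |
|---|---|---|
| Baseline | 8.1.11 / 8.2.1.17 | Before treatment |
| Cycle 4 | 8.2.2.14 | On treatment, if still receiving drug |
| End of treatment | Not in 8.3; nearest is 8.4 | Off treatment |

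**Step 2. Time from last dose to the 8.4 questionnaire.** Inputs: doses on Days 1 and 15 of a 28-day cycle (10.1); visit 4-6 weeks after Day 28 of the final cycle (8.4).

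Days since last dose = (28 − day of last dose) + 7 × weeks.

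- Last dose on Day 15: 13 + 28 = 41 days, to 13 + 42 = 55 days.
- Last dose on Day 1 of the final cycle: 27 + 28 = 55 days, to 27 + 42 = 69 days.

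**Step 3. What the questionnaire covers.** Appendix XII uses a 7-day recall. In the shortest case the recall period starts 41 − 7 = 34 days after the last dose, more than two 14-day dosing intervals. Even if a site counted 4 weeks from the last dose itself, the visit would fall at 28 days and the recall period would start at 28 − 7 = 21 days, still beyond one dosing interval. On no reading does the score reach back to the treatment period.

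**Step 4. When the on-treatment score first becomes available.** Nominal study day of Cycle 4 Day 15 = 3 × 28 + 15 = 99. The window closes on Cycle 5 Day 15 = 4 × 28 + 15 = day 127. Delayed cycles move both later. Section 4.5 removes participants for progression after 2 or more cycles. An assessment on Cycle 3 Day 1 is nominal day 2 × 28 + 1 = 57, which is 99 − 57 = 42 days before the first possible on-treatment score. A participant removed then has none.

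**Step 5. Consequence for the GEE.** Ordinary unweighted GEE relies on scores being missing completely at random. Absence at Cycle 4 because of progression or toxicity is unlikely to meet that condition. How many participants this affects, and by how much their scores differ, cannot be obtained from the documents.

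**The case against.** The best reply is that this is loose labelling. Section 10.5 names three time points and the schedule contains three collections, so no planned score is lost. Section 10.5 also states its aim more broadly, as quality-of-life change after baseline, which a post-treatment score fits. Renaming the third time point would remove the contradiction. That is correct as far as it goes, and it is the fallback below. It would not give early leavers a score close to treatment, which the objective in 1.3 calls for.

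The general instruction in 8.3 to complete evaluations promptly at discontinuation does not settle the matter, because the list that follows and the Appendix I column both omit the questionnaire.

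A reader might be tempted to go further in four ways. The documents support none of them.

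- **That the objective cannot be met at all.** The Cycle 4 score does measure quality of life on treatment.
- **That the GEE estimate is biased towards participants doing well.** Selection at Cycle 4 could push that way, but off-treatment scores, possibly after progression, could push the other way. Section 8.4 asks for all participants to be seen, so early leavers can still contribute a late score. Section 10.5 does not say how time is coded or which contrast is reported.
- **That drug clearance by the time of the visit shows benefit has been lost.** Nothing in the documents links serum level to quality of life.
- **That the 8.4 score should be dropped.** It is useful scheduled data; only its label is wrong.

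It also stands that the endpoint is exploratory, the trial has at most 20 participants, and the decision rule in 10.2 does not use quality of life.

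**Conclusion.** The mismatch is real and appears in both the visit text and Appendix I. The third time point in 10.5 has no matching collection at discontinuation. The score that would take its place is obtained 41-55 days after a Day 15 last dose, or 55-69 days after a Day 1 last dose, and so measures quality of life off treatment. Change on treatment rests on Cycle 4 alone, and only for those still receiving drug at about day 99. The estimate may be selective, but the net direction and size of any bias cannot be determined.

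These figures assume nominal 28-day cycles and the count in 8.4 from Day 28 of the final cycle. The conclusion does not depend on that count, since the score is still off treatment if the count starts at the last dose. The trial's primary conclusions are unaffected. The point is worth acting on because the correction is specific and cheap.

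**What to change.** Add the FAHI+KS to the procedure list in 8.3 and to the Treatment Discont. column of Appendix I. In 10.5, define the end-of-treatment value as that score, and enter the 8.4 score in the GEE as a separate, post-treatment time point.

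If discontinuation visits have already passed, relabel the third time point in 10.5 as post-treatment, base the on-treatment estimate on Cycle 4, and report how many participants contribute at each time point. This needs wording only.

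The cost of the main change is one more questionnaire at an existing visit, plus the amendment text. It has a limit: discontinuation scores will fall at different cycles and follow different events (progression, toxicity, complete response or completion of 12 cycles), so the cycle and reason should be reported alongside them. It also leaves the Cycle 4 score available only for those who remain on treatment.
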